The SAKURA development program is a multinational, multicenter, randomized, double-masked protocol (Santen Protocol 32-007) assessing the safety and efficacy of three doses of DE-109 (44 µg, 440 µg and 880 µg) administered every 2 months in subjects with active, non-infectious uveitis of the posterior segment of the eye. A planned unmasked analysis of 6-month data of 347 subjects has been completed. In the analysis, both the 440 µg and 880 µg doses of DE-109 demonstrated efficacy in the treatment of non-infectious uveitis affecting the posterior segment of the eye. The 440 µg dose demonstrated statistically significant differences for the primary and key secondary endpoints when compared to the 44 µg dose. Efficacy results for the 880 µg dose regimen were not as significant compared to the 44 µg dose. Additionally, there was a tendency towards increased reporting of AEs associated with intraocular inflammation following intravitreal administration with the 880 µg dose. In the overall analysis, the 440 µg dose demonstrated a more favorable Benefit-Risk profile than the 880 µg dose. The SAKURA development program is on-going and continues to enroll.

This study (Santen, Protocol 32-009) is being initiated to allow subjects continued access to DE-109 (440 µg) following participation in the SAKURA program and to obtain additional long-term safety data on the to be developed dose.

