**12.2.5. Vitreous Haze**

VH will be assessed for each eye at each visit using the modified SUN scale scores of: 0, 0.5+, 1+, 1.5+, 2+, 3+, 4+.

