### **14.6. Safety Analysis**

The safety assessments will include the incidence of AEs and SAEs and treatment with rescue therapy. Changes in BCVA, IOP, indirect ophthalmoscopy variables and VH will also be used to evaluate the long-term safety of DE-109. Safety data from both eyes will be included.

Each AE will be classified into a system organ classification (SOC) and coded to a preferred term using the most updated version of MedDRA ([MedDRA 16.0, 2013](#)). Subjects with any AE(s) will be tabulated by SOC and preferred term. They will also be tabulated by SOC, preferred term, and maximum severity. In these AE tables, a subject who experienced multiple AEs within a SOC or preferred term will be counted only once at the maximum severity for that SOC or preferred term; in addition, ocular AEs will be presented first to be separated from non-ocular AEs. Study-medication-related and injection-procedure-related AEs will be summarized similarly. In addition, AEs, SAEs, and AEs leading to discontinuation and death, if any, will be listed. ESIs, if any, will also be listed by event type.

Ocular safety outcome measures will be summarized using descriptive statistics. Specifically for BCVA, IOP, indirect ophthalmoscopy findings, and VH, scores and changes from baseline will be summarized descriptively; in addition, clinically significant changes from baseline, if any, will be listed.

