#### **21.4.6. Vitreous Haze**

VH will be assessed for each eye according to the Investigator's standard practice at Day 1, Month 12 and Post-Baseline PRN Treatment Visits using the modified SUN scale:

0	No inflammation
0.5+	Trace Inflammation (slight blurring of the optic disc margins and or loss of nerve fiber layer reflex)
1+	Mild blurring of the retinal vessels and optic nerve
1.5+	Optic nerve head and posterior retina view obstruction greater than 1+ but less than 2+
2+	Moderate blurring of the optic nerve head
3+	Marked blurring of the optic nerve head
4+	Optic Nerve head not visible

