#### 4.1.5. Analysis Visit and Analysis Window

*Analysis visit* is a timing variable to be used for tables and listings involving visits. In SPRING study, possible values of analysis visit include Baseline, Month 2, Month 4, Month 6, Month 8, Month 10, and Month 12. The *analysis window* will be used to determine the analysis visit of an assessment based on the study day of the assessment. The analysis window usually is slightly wider than the corresponding assessment window specified in the protocol for analysis purposes. Table 2 shows the analysis windows for post-baseline visits in SPRING study. Detailed definitions of analysis visit and analysis window will also be provided in the ADaM specifications document.

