## **8.2. Vitreous Haze (VH)**

VH score, change from baseline, and shift from baseline in VH at Month 12 visit and Study Exit visit will be summarized and listed.

Subgroup analysis will be performed for change from baseline in study eye at study exit by demographics and baseline characteristics in [Section 7.2](#).

Subjects with any score of 3+ or above in VH after Baseline will be listed.

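### Before exit, SAP 8.2 reports vitreous haze only through a 3+ listing that ignores baseline, so a transient worsening below 3+ reaches no VH output

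*SAP*

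**What the plan says.** The protocol counts change in VH among its safety parameters (12.2 and 14.1.1). Section 14.6 says that scores and changes in BCVA, IOP, ophthalmoscopy findings and VH will be summarised, and continues: "in addition, clinically significant changes from baseline, if any, will be listed". It does not define clinical significance and does not limit that listing to the exit visit.

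On collection, protocol 21.4.6 states: "VH will be assessed for each eye according to the Investigator's standard practice at Day 1, Month 12 and Post-Baseline PRN Treatment Visits". For subjects under US Amendment 01, SAP Table 1 also schedules VH at Months 2, 4, 6, 8 and 10, whether or not an injection is given (SAP 4.1.4). SAP 4.1.5 provides the time frame for these readings: "possible values of analysis visit include Baseline, Month 2, Month 4, Month 6, Month 8, Month 10, and Month 12". PRN and unscheduled visits are mapped into those windows.

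On reporting, SAP 8.2 says: "VH score, change from baseline, and shift from baseline in VH at Month 12 visit and Study Exit visit will be summarized and listed". Its subgroup analysis is also at study exit. The one remaining VH output is: "Subjects with any score of 3+ or above in VH after Baseline will be listed".

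**The concern.** The protocol commits to listing changes, and the SAP delivers a listing of levels. The two differ in both directions: a clear rise that stays below 3+ is not picked up, and an eye that entered with severe haze and never worsened is.

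The readings taken between Day 1 and exit are collected, checked and mapped to analysis windows, but they feed nothing except the 3+ listing. In a descriptive safety study without hypotheses, the planned tables and listings are the result, so a measure left out of them goes unreported. The background gives some reason to look at inflammation: protocol section 5 says of the 880 µg dose in the parent programme that "there was a tendency towards increased reporting of AEs associated with intraocular inflammation following intravitreal administration". This extension was set up partly to gather long-term safety data at 440 µg.

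**Working it through.** The plan gives no figure on this point to reproduce. The check is a comparison of rules and a count of patterns.

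**1. Which visits the summaries cover.** SAP 4.1.2 defines Study Exit as the Month 12 or early termination visit. SAP 4.1.5 uses the latest Month 12 visit for VH. For a completer, Month 12 and Study Exit are therefore one visit, and the score, change and shift outputs describe one post-baseline time point.

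**2. How the same SAP treats neighbouring measures before exit.**

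| Measure | Rule at visits before exit | Uses baseline? |
|---|---|---|
| IOP (8.4) | Rise of at least 10 mmHg from baseline at any post-baseline visit, tabulated and listed | Yes |
| Ophthalmoscopy (8.5) | Normal at baseline to abnormal later, listed | Yes |
| VH (8.2) | Score of 3+ or above, listed | No |

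**3. What the 3+ rule picks up.** Inputs: the seven levels 0, 0.5+, 1+, 1.5+, 2+, 3+, 4+ (protocol 12.2.5), and the listing rule applied to the highest score before exit.

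- Possible worsenings: C(7,2) = 21.
- Worsenings that end at 2+ or below, and so are missed: C(5,2) = 10. Listed: 21 − 10 = 11.
- Of the 10 missed, 4 are single steps, so 10 − 4 = 6 span two or more levels: 0 to 1+, 0 to 1.5+, 0 to 2+, 0.5+ to 1.5+, 0.5+ to 2+, and 1+ to 2+.
- Listed without any worsening: 3 patterns (3+ to 3+, 4+ to 4+, 4+ to 3+).

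Measured in score units instead of levels, the rule misses 6 of 17 rises of at least 1, 3 of 12 of at least 1.5, and 1 of 9 of at least 2. That last one is 0 to 2+, which is four steps up the scale.

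**4. What a change rule would pick up.** A shift table to the worst post-baseline score shows all 21. A listing at two or more levels takes in 21 − 6 adjacent steps = 15. Together with the retained 3+ listing, which adds 2+ to 3+ and 3+ to 4+, it takes in 17. The four left out are single steps ending at 2+ or below, and the shift table still shows them.

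**5. Scale in subjects, as illustration only.** The documents give no rate of transient rises. Suppose a share p of the 60 subjects (SAP 3.3) had a recorded rise from 0 to 2+ that settled by exit. The expected number absent from VH outputs is 60p, and the chance of at least one is 1 − (1 − p)^60.

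| Assumed p | Expected subjects | Chance of at least one |
|---|---|---|
| 2% | 1.2 | 70% |
| 5% | 3 | 95% |
| 10% | 6 | 99.8% |
| 20% | 12 | >99.9% |

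**The case against.** Three stronger readings are tempting, and the documents support none of them.

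- A reader might infer that such a rise would appear in no safety output at all. That goes too far. Protocol 12.1.1 treats a significant change from baseline as an AE, and its exception for lack of efficacy ends where the investigator assesses a clinically significant change. SAP 8.1 tabulates and lists all on-study AEs, with ocular AEs shown separately. SAP 8.7 lists qualifying rescue and counts it in the rescue rate. A rise still present at the last visit is in the exit shift. What remains is that AE reporting rests on judgment with no VH threshold, and that topical corticosteroid is not rescue (SAP 4.5.1), so neither route is assured.
- A reader might take intraocular inflammation to be an established dose-related risk here. Protocol section 5 reports only a tendency in AE reports at 880 µg, a dose not given in this study, and inflammation is not among the events of special interest.
- A reader might say that the plan misses post-injection inflammation. VH is not repeated after dosing; only ophthalmoscopy, IOP and AEs are (protocol 7.5.3). Under the protocol, most readings before exit are taken at retreatment visits at least 60 days after the last dose. A rise there may equally be recurrent uveitis. Only 13 of the 60 subjects came under US Amendment 01, with its scheduled visits, so for the other 47 a flare may also go unmeasured. Reporting cannot repair that.

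Two further points stand. The pattern count gives every transition equal weight and says nothing about frequency. A cut of two levels has no source in the documents and treats unequal steps alike. Neither removes the mismatch between protocol 14.6 and SAP 8.2.

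**Conclusion.** The point holds as a reporting gap specific to VH. Before exit, SAP 8.2 offers a listing by absolute level where the protocol promises one by change from baseline, and it treats VH less well than the SAP treats IOP. The size is 10 of 21 possible worsenings missed and 3 non-worsening patterns listed. The number of subjects affected cannot be derived from the documents.

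This rests on two assumptions: that SAP 8.2 states all planned VH outputs, and that the rise is recorded at a visit and has settled by exit. It is a modest point in a descriptive study of 60 subjects, worth acting on because the data are already in hand.

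**What to change.** In SAP 8.2, for study eye and fellow eye:

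1. Add a shift table from baseline to worst post-baseline VH at any visit.
2. Add a listing of subjects whose increase from baseline meets a threshold fixed before database lock. At least two scale levels is one example. State it in levels, and as the SAP's definition of the term that protocol 14.6 leaves undefined.
3. Keep the 3+ listing, with the baseline score shown beside each entry.
4. Give the number of VH readings per subject.

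The cost is one table, one new listing and an extra column, all on data already collected, with no change to study procedures. The downside is that an any-visit result depends on how often a subject was read, which follows how often the subject was retreated. It also cannot separate recurrent uveitis from drug-related inflammation. The output should therefore be labelled as worsening at a post-baseline visit, not as post-injection inflammation.

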## **8.3. Best-Corrected Visual Acuity (BCVA)**

BCVA and change from baseline in BCVA at Month 12 and Study Exit visit will be summarized and listed.

Subjects with improvement or worsening of at least 5 letters, 10 letters, or 15 letters in study eye at Month 12 visit will be tabulated, as well as subjects maintained BCVA within 5 letters of change in study eye.

Subjects with any BCVA score of 0 after baseline will be listed.

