## 12. ASSESSMENT OF SAFETY

### 12.1. Adverse Events, Serious Adverse Events and Events of Special Interest

#### 12.1.1. Definition of Adverse Events

An AE is any untoward medical occurrence in a subject administered a pharmaceutical product and which does not necessarily have a causal relationship with study drug. An AE therefore can be an unintended sign (including an abnormal laboratory finding), symptom, or disease temporally associated with the use of a medicinal (investigational) product, whether or not related to the medicinal (investigational) product.

In clinical studies, an undesirable medical condition occurring at any time, including baseline or wash-out period, may be recorded as an AE even if no study drug has been administered.

Any significant change in a subject's condition from baseline, regardless of causality, is to be considered an AE, unless the change is determined to be a continuation of a pre-existing condition that is documented in the subject's medical history. However, a clinically significant worsening in severity, intensity, or frequency of a pre-existing condition may indicate an AE.

Lack of efficacy of the study drug for the condition being investigated is not considered an AE unless a clinically significant change is assessed by the Investigator. In addition, any elective surgical procedure scheduled or planned prior to study entry is not considered an AE and the underlying diagnosis for which surgery is to be performed should be captured in the medical history as a pre-existing condition.

For this protocol, an AE is any *on-study* untoward medical occurrence (e.g. sign, symptom, disease, syndrome, intercurrent illness) that occurs in a study subject, regardless of the suspected cause and regardless of timing of DE-109 (440 µg) administration. An on-study AE can occur anytime after the date of informed consent through the last study visit. An AE will be considered as *treatment-emergent* if the AE occurred on or after the date of the first DE-109 (440 µg) treatment up to the last study visit. Treatment-emergent AEs are a subset of on-study AEs. Both on-study and treatment-emergent AEs will be reported.

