## 2. STUDY OBJECTIVE

The objective of this extension study is to evaluate the long-term safety of treatment with DE-109 (440 µg) in subjects with non-infectious uveitis of the posterior segment of the eye.

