### 4.2.3. Change from Baseline

The *change from baseline* in a measure at a post-baseline visit will be derived as:

Change from Baseline at a Post-Baseline Visit = (Score at the Post-Baseline Visit) – (Baseline Score).

For any measure assessed before and after injection at visits, only the pre-injection scores will be used to derive the change-from-baseline variable.

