**Table 3 Other Safety Assessments**

Safety Measures	Note
Slit-lamp Biomicroscopy: Vitreous haze	VH is assessed for each eye using the modified SUN scale as 0, 0.5+, 1+, 1.5+, 2+, 3+, or 4+. A decrease in VH score

	indicates improvement in the vitreous inflammation.
Best-corrected visual acuity	BCVA measures the acuteness or clearness of best-corrected vision in ETDRS letters (e.g., 75 letters). An increase in BCVA indicates improvement in the best-corrected vision. A 5-letter difference in visual acuity is equivalent to one Snellen line. A BCVA score of 85 ETDRS letters is equivalent to 20/20 vision, which is considered normal vision.
Intraocular pressure (IOP)	IOP, the fluid pressure inside the eye, is recorded in mmHg with one decimal point (e.g., 24.0 mmHg). If DE-109 is administered, a second assessment of IOP is made after injection.
Indirect ophthalmoscopy: lens and cataract	The lens of an eye is classified as Phakic, Aphakic, or Pseudophakic. Phakic lens is assessed for the presence of cataract (Yes or No).
Indirect ophthalmoscopy: Retina, macula, choroid, optic nerve	Retina, macula, choroid, and optic nerve, if able to be assessed, are graded as Normal or Abnormal. If DE-109 is administered, these ophthalmoscopy parameters are performed again after injection.
Slit-lamp biomicroscopy a : Lid Hyperemia, Lid Edema, Conjunctival Hyperemia, Chemosis, Corneal Edema, Conjunctival Discharge Exudate, Anterior Chamber Flare	The status of each of these biomicroscopy parameters is rated as 0 = None, 1 = Mild, 2 = Moderate, or 3 = Severe. For each abnormal record, the clinical significance (Clinically Significant or Not Clinically Significant) is also determined.
Slit-lamp biomicroscopy a : Pupil, Lashes, Ocular Motility, Iris	The status of each of these biomicroscopy parameters is determined as Normal or Abnormal. For each abnormal record, the clinical significance (Clinically Significant or Not Clinically Significant) is also determined.
Slit-lamp biomicroscopy a : Vitreous Cell Count	This measure is rated as 0 = 0 cells, 0.5+ = 1-10 cells, 1+ = 11-20 cells, 2+ = 21-30 cells, 3+ = 31-100 cells, or 4+ = $\geq 100$ cells.
Slit-lamp biomicroscopy a : Anterior Chamber Cell	This measure is rated as 0 = <1 cell, 0.5+ = 1-5 cells, 1+ = 6-15 cells, 2+ = 16-25 cells, 3+ = 26-50 cells, or 4+ = $\geq 50$ cells.

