## 6.2. Handling of Missing Data

### 6.2.1. Safety Measures

Descriptive summaries of safety measures will be based on observed data only. No imputation of missing scores will be implemented.

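### SAP 8.3 tabulates BCVA change without regard to lens removal during SPRING, so a cataract loss reversed by surgery can be counted as maintained or improved vision

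*SAP*

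**What the plan says.** **BCVA outputs.** SAP 8.3 states that "BCVA and change from baseline in BCVA at Month 12 and Study Exit visit will be summarized and listed". It then adds the categories: "Subjects with improvement or worsening of at least 5 letters, 10 letters, or 15 letters in study eye at Month 12 visit will be tabulated". A further category counts study eyes whose score stayed close to baseline, with 5 letters as the limit. The only other output in that section is a listing of subjects with a score of 0 after baseline. SAP 4.2.3 defines change as the post-baseline score minus the Day 1 baseline score, and SAP 6.2.1 says "Descriptive summaries of safety measures will be based on observed data only". None of these sections mentions lens status or eye surgery.

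**Lens data.** SAP Table 3 records that "The lens of an eye is classified as Phakic, Aphakic, or Pseudophakic". Ophthalmoscopy, which includes the lens, is scheduled at Day 1, PRN treatment visits and Month 12 (protocol Table 3 and 12.2.4). The analyses use lens status only to restrict cataract summaries to phakic eyes: the baseline characteristic in SAP 7.2 and the exit shift table in SAP 8.5. SAP 8.5 also lists subjects who go from no cataract to cataract. The only eye operation that the safety analyses name is vitrectomy, in the rescue section (SAP 8.7).

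**Surgery.** Protocol 8.2 excludes ocular surgery in the 30 days before entry. Lens removal during the study is not among the prohibited treatments in 9.2.1 or the withdrawal reasons in 8.3. Protocol 12.1.1 adds that "any elective surgical procedure scheduled or planned prior to study entry is not considered an AE"; the diagnosis behind such surgery goes into the medical history.

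**The concern.** Long-term safety is the sole objective (SAP 2), and BCVA is one of its main ocular measures. Lens removal can change the BCVA score for reasons unrelated to how the eye fared up to that point. If a phakic study eye loses letters to cataract, is operated on and is then refracted to best correction, the Month 12 table takes only the score after surgery. The loss that led to the operation is not in the table.

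The other BCVA output does not recover it, since a listing of scores of 0 catches only extreme loss. The SAP treats other measures differently: IOP thresholds are assessed at any post-baseline visit (8.4), and vitreous haze of 3+ or above at any time after baseline is listed (8.2). BCVA has no comparable any-visit output for loss.

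The eye can also leave the cataract table. The exit shift in SAP 8.5 covers phakic lenses only, so an eye that is pseudophakic or aphakic at exit is not in it. A reader could then see stable vision in one table and no worsening of cataract in another, for an eye whose lens was removed because of cataract.

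**Working it through.** The plan states no figure on this point, so there is none to reproduce. The check applies the SAP's own rules to illustrative eyes and then scales the result to the study size.

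**Step 1: classification.** Change = Month 12 score − baseline score (SAP 4.2.3), sorted by the SAP 8.3 categories. The letter scores are invented for illustration.

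| Baseline | Before surgery | Month 12 | Interim change | Month 12 change | 8.3 category |
|---|---|---|---|---|---|
| 70 | 50 | 70 | −20 | 0 | maintained |
| 70 | 50 | 78 | −20 | +8 | improved by at least 5 |
| 55 | 45 | 75 | −10 | +20 | improved by at least 15 |
| 70 | 50 | 62 | −20 | −8 | worsened by at least 5 |
| 70 | 38 | 70 | −32 | 0 | maintained |

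The first three eyes lose letters and are then counted as maintained or improved. The fourth is still counted as worse, so this does not happen to every operated eye. The fifth is maintained in 8.3, but its interim loss exceeds 30 letters and would be reported separately as a sight-threatening event (SAP 4.4.1.2.1). No interim change in the table appears in an 8.3 output.

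**Step 2: size per operated eye.** n = 60 (SAP 3.3). The number of operated eyes k and the letter difference due to surgery g are assumptions.

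- Largest category shift = k/60: 1.7 percentage points for k = 1, 5.0 for k = 3, 10.0 for k = 6. If only 45 subjects reached Month 12 (assumed), one eye would be 1/45 = 2.2 points.
- Shift in mean change = k × g/60. With g = 15: 0.25 letters for k = 1, 0.75 for k = 3, 1.5 for k = 6. Across g = 10 to 25 the range is 0.17 to 0.42 letters for k = 1 and 1.0 to 2.5 for k = 6.
- With k = 0 both are zero.

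**Step 3: how likely is k ≥ 1?** P(k ≥ 1) = 1 − (1 − p)^60. For assumed 12-month rates p of 2%, 5% and 10%, the expected counts are 1.2, 3.0 and 6.0, and the probabilities are 0.70, 0.95 and above 0.99.

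**Step 4: would the last score before surgery repair the table?** Of 60 subjects, 13 consented to US Amendment 01 (SAP 3.3), and the Month 2 to 10 visits apply only to them (SAP Table 1, footnote h). The other 60 − 13 = 47 have scheduled study BCVA only at Day 1, injection visits and Month 12. If an operated eye had no post-baseline reading before surgery, its last earlier score is Day 1 and its change is 0 by construction.

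Take six operated eyes, each truly at −20 before surgery and +5 at Month 12, with the other 54 averaging −3:

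- Observed: (54 × −3 + 6 × 5)/60 = −2.2.
- Pre-surgery readings exist: (54 × −3 + 6 × −20)/60 = −4.7.
- Only Day 1 exists: (54 × −3 + 6 × 0)/60 = −2.7.

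In the last case all six eyes are again scored as maintained, which is the problem that the table was meant to solve.

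**The case against.** The strongest reply is that the safety signal is largely captured elsewhere. A significant change from baseline is an adverse event unless it continues a documented condition (protocol 12.1.1). Ocular events are summarised and listed (SAP 8.1), new cataract is listed (8.5), a loss of 30 letters or more is a sight-threatening event, and protocol 14.6 promises a listing of clinically significant BCVA changes. Where surgery was planned before entry, the diagnosis belongs in the medical history, eye disorders ongoing at baseline are tabulated (SAP 7.3), and exclusion criterion 6 on other sight-compromising eye disease may narrow that group. All of this stands. A reader might infer that surgery hides the cataract altogether; the documents do not support that. What is missing is the link: none of these outputs shows which eyes in the BCVA categories had their lens removed. The new-cataract listing also omits a baseline cataract that worsens and is removed, and the SAP sets no threshold for the protocol 14.6 listing.

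A second reply is that reporting observed vision whatever followed is a legitimate choice in a single-arm descriptive study, and that rescue therapy can also affect BCVA. That stands too, and is why the observed table should stay. Rescue, however, has its own definition, rate and listing (SAP 4.5.1 and 8.7), while lens removal has none.

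A third reply is that a table based on the last pre-surgery score fails on this study's visit schedule. Step 4 of the working bears this out.

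**Conclusion.** The gap is real and moderate. SAP 8.3 has no rule for lens removal during SPRING, so an operated eye can be counted as maintained or improved after a cataract loss, and the same eye drops out of the exit cataract shift table if it is no longer phakic.

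Three stronger readings are not supported. Such an eye is not always counted favourably: one still more than 5 letters below baseline counts as worse. The table does not describe vision on DE-109 as such, because the Safety Population includes subjects never injected in SPRING (SAP 5.1), and without a comparator no version of 8.3 isolates the drug's effect. A bias in one direction is plausible but not shown, since neither document reports BCVA after lens surgery.

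The size is unknown. It is at most 1.7 percentage points per operated eye in any one category at n = 60, more if fewer subjects reach Month 12, and zero if no eye is operated on. The rates and letter gains in the working are assumptions. No hypothesis test or error rate is affected. What is at stake is whether a main ocular safety table can be interpreted.

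**What to change.** Keep the observed summary in SAP 8.3 as it is, and add:

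1. BCVA change at Month 12 and Study Exit, and the 5, 10 and 15-letter categories, shown separately for study eyes with and without on-study lens removal. Define lens removal as lens status changing from phakic to pseudophakic or aphakic after Day 1, or a recorded procedure.
2. A listing of the operated study eyes with baseline BCVA, any post-baseline BCVA before surgery, and exit BCVA. Where no such pre-surgery reading exists, show it as not available, not as a change of 0.
3. In the SAP 8.5 exit shift table, a row for eyes phakic at baseline that became pseudophakic or aphakic.

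Do not make a carry-forward of the last pre-surgery score a main remedy, for the reason in Step 4 of the working.

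The cost is SAP wording, one split table, one short listing and one table row. The split can be made from baseline and exit lens status, which are already recorded. The downside is that the operated group will be small, so its summary will be sparse and the listing will carry most of the information.
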